# **Sensory Integration of Auditory and Visual Cues in Diverse Contexts**

## **Statistical Analysis Plan**

**June 1st, 2020**

**NCT04479761**

For each of measure of interest and for each environment (stars, subway), we will fit a linear mixed effects model. Each model will include main effects of group, visual condition, and auditory condition, as well as all two and three-way interactions. The models will also control for age. For aim 1, we will assess the significance of contrasts between no sounds / dynamic sounds for the different visual conditions and groups. For aim 2, the same will be done for contrasts between no sounds / static sounds. These models estimate the difference in visual weighting and reweighting between the groups, maximizing the information we can obtain from the data by accounting for the inherent multi-level study design (person, conditions, repetitions). Since each person completes various trials for each condition, the linear mixed effects model accounts for these sources of variability. *P*-values for the fixed effects will be calculated using the Satterthwaite approximation for the degrees of freedom for the T-distribution.

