Sensory Integration of Auditory and Visual Cues in Diverse Contexts

Study Protocol

June 1st, 2020

NCT04479761

The same sample of adult participants (18 or older) will be recruited to study both specific aims. All participants will have normal or corrected to normal vision and no peripheral neuropathy or other neurological conditions. Control participants will be recruited from the NYU community, and registry of alumni, local fitness centers and local senior centers. The two patients' groups will be recruited from the Ear Institute of Mount Sinai.

Group 1: Unilateral peripheral vestibular hypofunction and normal hearing, e.g., vestibular neuritis. Potentially eligible participants with a functional complaint of head motion provoked instability or dizziness affecting their functional mobility and quality of life will be identified by key personnel and additional staff at the Ear Institute during their standard clinical evaluation. They will present with at least one positive finding indicating unilateral vestibular hypofunction on the following clinical tests: head thrust, subjective visual vertical and horizontal, post head shaking nystagmus, spontaneous and gaze holding nystagmus⁸⁴ in addition to a score of at least 16 (mild handicap) on the Dizziness Handicap Inventory (DHI).⁷¹ Unilateral peripheral vestibular hypofunction will then be confirmed by the meeting at least one of the following diagnostic criteria:^{2,85}

- 25% or above unilateral weakness on caloric testing⁷⁰;
- Low gain on vHIT <.8;⁸⁶
- Ocular Vestibular evoked myogenic potential (oVemp) amplitude asymmetry greater than 34%;
- Cervical (cVemp) amplitude asymmetry greater than 40%.

Patients will be excluded if they are diagnosed with an unstable peripheral lesion, e.g., Meniere's Disease, Perilymphatic Fistula, Superior Canal Dehiscence, or Acoustic Neuroma.

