Videonystagmography (VNG): The VNG caloric test requires the participant to wear goggles that allow careful monitoring of eye movement in response to hot and cold air placed in the ear canal.

[figure not shown]
Audiogram: The participant wears headphones and is asked to identify sounds at different frequencies and repeat simple words.

Video Head Impulse Test (vHIT): The vHIT requires the participant to wear special goggles and focus on a target on the wall. The examiner will move that participant's head right, left, up, down and diagonal while he/she keeps their eyes on the target.

The session is expected to take 2 hours.

Postural Control session (NYU Physical Therapy Department, Arthur J. Nelson Jr., Human Performance Laboratory, could be split into 2): Participants will complete 4 self-reported questionnaires as described under 'materials' below (they can complete it at home prior to the session as well if they prefer). The participants will be wearing a virtual reality headset (HTC Vive) and bluetooth-connected headphones (Bose). They will complete a series of standing tasks while observing a virtual display and listening to sounds. They will be asked to stand with their feet hips-width apart. The variations of visuals and sounds are explained in Table 1 below. All conditions will be randomized. Sounds will be displayed at the highest level that is comfortable to the participant. Scenes are 60 seconds long. We have a total of 12 combinations: 2 environments (stars, subway) X 2 visuals (moving, static) X 3 sounds (moving, none, static) and each combination will be repeated 3 times for a net testing time of 36 minutes. Including rest breaks, total testing time is expected to take no longer than 2 hours could be completed over 2 sessions. For aim 1, we will assess the significance of contrasts between no sounds / dynamic sounds for the different visual conditions and groups. For aim 2, the same will be done for contrast between no sounds / static sounds.

Table 1. Protocol for the 2 specific aims.

The environment	Visuals	Sounds
An abstract display of star wall 	Static stars Moving stars: 0.2 Hz, 0.032m, Anterior-Posterior (AP)	No sound Static White Noise Moving Sound: white noise circling around the participant

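### Do the sound contrasts assigned to aims 1 and 2 leave the between-group difference untested?

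*SAP*

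**What the plan says.** The SAP is one unnumbered paragraph. For each measure and environment it fits a linear mixed model with "main effects of group, visual condition, and auditory condition, as well as all two and three-way interactions", and also controls for age. It then assigns tests to the aims: "For aim 1, we will assess the significance of contrasts between no sounds / dynamic sounds for the different visual conditions and groups". For the second aim: "For aim 2, the same will be done for contrasts between no sounds / static sounds". The Protocol, under the Postural Control session, says the same and adds no group comparison.

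The next SAP sentence gives the purpose of the models: "These models estimate the difference in visual weighting and reweighting between the groups". It does not say which model term carries that difference or which aim it serves. The paragraph ends with p-values "for the fixed effects will be calculated using the Satterthwaite approximation for the degrees of freedom for the T-distribution".

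The design in the Protocol is "2 environments (stars, subway) X 2 visuals (moving, static) X 3 sounds (moving, none, static) and each combination will be repeated 3 times". There are three groups: unilateral vestibular hypofunction, unilateral hearing loss, and controls. The Protocol's opening paragraph has one sample serve both aims. The aims themselves are not written out in either document; only their contrasts are.

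**The concern.** The plainest reading of the aim sentences is a simple effect of sound in each combination of group and visual condition. Each such contrast uses one group only, so however many are significant, none tests whether groups differ. Yet the SAP describes the models as estimating a group difference. If no interaction contrast is tied to an aim, a reader might conclude that groups differ because sound was significant in one and not in another. That inference is unsound: two groups with the same true effect can easily fall on opposite sides of a significance threshold. At stake would be the study's central comparison of patients with controls.

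**Working it through.** **Inputs.** From the documents: 3 groups, 2 visual conditions, 3 sound conditions, 2 environments, 3 repetitions, 60-second scenes. Not given: sample size, SD, effect size, alpha, factor coding. There is therefore no inferential figure to reproduce. The one design figure checks: 2 × 2 × 3 = 12 combinations, and 12 × 3 × 1 minute = 36 minutes.

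**Counts.** One model has 3 × 2 × 3 = 18 cell means (age aside). Per aim, measure and environment:
- within-cell sound contrasts: 3 × 2 = 6 (12 over both environments);
- patient-versus-control contrasts of the sound effect: 2 × 2 = 4;
- three-way patient-versus-control contrasts: 2.

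**Which group differences already have a p-value.** Assume treatment coding with controls, static visuals and no sound as reference. Let S be the coefficient of the aim's sound, V that of moving visuals, and G that of a patient group; products denote interactions.

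| Quantity, patient group minus controls | Expression | Single coefficient? |
|---|---|---|
| Moving minus static visuals, no sound (visual weighting) | (V + GV) − V = GV | Yes |
| Change in moving minus static from no sound to sound (reweighting) | (VS + GVS) − VS = GVS | Yes |
| Sound minus none, static visuals | (S + GS) − S = GS | Yes |
| Sound minus none, moving visuals | (S + VS + GS + GVS) − (S + VS) = GS + GVS | No, a sum of two |

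The first two rows are the natural translation of the SAP's purpose sentence, and planned fixed-effect p-values cover both. The only uncovered row is the last: 2 of the 4 group-by-sound contrasts per aim. It is a linear combination of terms already in the fit and concerns response to sound, not visual weighting.

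**Size of the feared error (illustration only).** If group differences were read from cell-wise significance, two independent groups with the same true effect and within-group power p would disagree with probability 2p(1 − p):
- p = 0.05 or 0.95: 2 × 0.05 × 0.95 = 9.5%;
- p = 0.20 or 0.80: 2 × 0.20 × 0.80 = 32%;
- p = 0.50: 2 × 0.50 × 0.50 = 50%.

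A single direct contrast errs 5% of the time at an assumed two-sided 0.05. These rates apply only if that practice is used. The SAP does not state it.

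**What the direct contrasts cost in precision (assumed: residual SD 1, person-slope SD 0.3, 30 per group, equal groups).** The per-person variance of one sound contrast is 2/3 + 0.09 = 0.757.
- Within group: SE = √(0.757/30) = 0.159.
- Group by sound: SE = √(2 × 0.757/30) = 0.225, ratio 1.41.
- Three-way: SE = √(4 × 0.757/30) = 0.318 if slopes are independent across visuals, ratio 2.00; or √(4 × 0.667/30) = 0.298 if the slope is shared and cancels, ratio 1.88.

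Making interactions the principal tests in place of the cell-wise contrasts would therefore cost precision.

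**The case for a change.** The strongest case for a change is that a plan should name its tests. The fixed-effect p-values are tied to no aim. Their meaning depends on a coding that the SAP does not give; under another coding the same coefficients answer other questions. Two group-by-sound contrasts per aim have to be requested explicitly, and a comparison of the two patient groups with each other would be a difference of coefficients. Naming all this would take a few sentences and no new data.

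Part of this stands. The phrase about visual conditions and groups can mean effects within cells or a comparison across them, and the SAP does not settle which. My table does rest on assumed reference levels.

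Three things limit it. First, every contrast in question can be estimated from the model as specified, so coding affects labels and default output, not what can be tested. Second, the between-group sentence directly follows the two aim sentences and the model is a full factorial; both fit an intention to compare groups. Third, because the aims are not written out, the cell-wise contrasts may be exactly what they ask for. Demoting them to supportive status would change the objective without support in the documents.

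**Conclusion.** No change to the plan follows. It is true that no sentence assigns a group-interaction contrast to an aim, and that the 6 within-cell contrasts per aim, measure and environment compare no groups. But the interactions are fitted and p-values for the fixed effects are planned. With controls, static visuals and no sound as reference, these include the patient-versus-control tests of both visual weighting and reweighting. The remainder is 2 group-by-sound contrasts per aim under moving visuals, each a sum of two fitted coefficients and outside the quantity the SAP names.

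The discordance of 9.5% to 50% would need both the within-cell reading of an ambiguous phrase and an inference from cell-wise significance that the SAP does not propose. This is unwritten detail that an analyst can fill sensibly from the same model. The conclusion rests on the assumed coding and on group differences being reported from the interaction terms, as the SAP's purpose sentence implies.
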